8.5.4 Visit 3: Day of TKA

[figure not shown]
8.5.5 Visit 4: Daily In-Hospital Visits: (Visits 4a, b, c, etc.)

8.5.6 Visits 5-7: Weeks 1-3 Post-TKA

8.5.7 Visit 8: 4 weeks Post-TKA

8.5.8 Visits 9-10: Follow-up Visits

Visits will occur at 2 months (Visit 9) and 3 months (Visit 10) after TKA surgery.

[figure not shown]
8.5.9 Visit 11: 12 months post-TKA Visit

8.5.10 Unscheduled Visits/Lead Replacements

Subjects may require an unscheduled visit if they experience:

- a technical issue with the stimulation system that the clinical staff has difficulty resolving or desire adjustments to stimulation parameters. [REDACTED]
- desire assistance with a bandage change [REDACTED]
- require a lead [REDACTED]
- experience an adverse event which requires further evaluation by the clinical study staff.

8.6 Study Visit Windows

The acceptable windows for each encounter are listed below in **Table 1**.

Table 1 Study Visit Windows

Visit Number	Visit Name	Window
1	Consent and Randomization Visit	[REDACTED]
2	Lead Placement Visit ^T and Check-in Call	[REDACTED]
3	Day of TKA (POD 0) Visit	[REDACTED]
4a, b, c...	Daily in-hospital Visits	[REDACTED]
5	1 week post-TKA Call	[REDACTED]
6	2 weeks post-TKA Visit	[REDACTED]
7	3 weeks post-TKA Call	[REDACTED]
8	4 weeks post-TKA Visit (EOT ^T)	[REDACTED]
9	2 months post-TKA Call	[REDACTED]
10	3 months post-TKA Call	[REDACTED]
11	12 months post-TKA Call	[REDACTED]

^T Treatment Group (Group #1) Only

8.7 Study Duration

The duration of this study is expected to be 2 years. [REDACTED]

8.8 Early Termination

8.9 *Subject Compensation*

Subjects will receive [REDACTED] compensation for taking part in all study visits. Compensation will be based on the subject completing milestones within the study. The disbursement schedule will be as follows:

- [REDACTED] after the completion of Visit 1
- [REDACTED] after the completion of Visit 2
- [REDACTED] after the completion of each Visit 3, 4 (only one instance), 6, and 8
- [REDACTED] after the completion of each Visit 5, 7, 9 10, and 11

If a subject in Group #1 volunteers to participate in an additional Visit 2 (returns for another session of stimulation testing or for a lead replacement), the subject will receive an [REDACTED] compensation at the completion of that visit. All requirements for Visit 2 will be repeated.

[REDACTED]

9.0 *Data Management*

9.1 *Subject Screening and Identification Log*

A subject screening log will be completed at the investigational site for all subjects who were considered for the study. Those individuals who are excluded will be listed along with the reason for exclusion.

[REDACTED]

The Subject Identification log will be completed for subjects enrolled in the study.

9.2 *Data Collection*

Case Report Forms (CRFs) will be completed for each subject who signs an informed consent form up until the point of discharge from the study. CRFs will be completed and maintained in a fashion that is consistent with accepted Good Clinical Practices. All paper documents will be completed in permanent blue or black ink and all entries will be made in a legible fashion. If necessary, corrections will be made by using a single line strikeout with the initials and date of the person making the correction. The corrections will be made so as not to obscure the original data. Correction fluid or correction tape may not be used. All paper study documentation will be stored in a locked storage facility (either a locked office or a locked cabinet).

9.3 *Subject Numbering*

All subjects who sign an informed consent will be given a unique alpha - numerical Subject ID number.

[REDACTED]

9.4 Confidentiality of Data

Every effort will be made to protect subject confidentiality. Subject names and personal identifiers will not appear in any publications resulting from this work.

9.5

10.0 Data Analysis

All primary and secondary outcome data will be analyzed and reported.

10.1 Analysis of Outcomes and Exploratory Measures

A table of outcomes and exploratory measures to be collected during the study can be found in Appendix A.

“Average Pain” [REDACTED] will be measured daily in both groups for 7 days prior to Visit 2, for 7 days prior to the TKA, and for the first 4 weeks post-TKA. [REDACTED]

[REDACTED] An overall mean across all subjects for the first 4 weeks following TKA surgery will be calculated [REDACTED]. The average [REDACTED] score over the 4 weeks will be compared between Groups. [REDACTED]

[REDACTED]

At several visits, subjects will be asked to report their weekly "Average Pain" [REDACTED]. The mean [REDACTED] will be calculated and compared between the Groups.

Pain treatments and analgesic usage will be recorded. Changes in opioid usage may be calculated using morphine equivalent dosing (MED). [REDACTED]

[REDACTED] subjects taking opioids [REDACTED] will be queried for side effects associated with opioids. [REDACTED] These pain treatment and analgesic-related outcomes will be compared between the Groups.

Functional tests performed during the study will include the Timed Up and Go [REDACTED] and the Six-Minute Walk Test. The data from these tests will be analyzed [REDACTED]

[REDACTED]

Surveys performed during the study will include the [REDACTED] Patient Global Impression of Change (PGIC), time to meet recovery milestones, Inpatient Pain Management Experience Survey, Subject Satisfaction Survey, and Clinician Satisfaction Survey. [REDACTED]

Subjects will be asked to report the number of Physical Therapy Sessions they attended each week post-TKA. [REDACTED]

Throughout the study, subjects will answer questions to describe their pain distribution and stimulation-evoked comfortable sensation (Group #1 only) coverage. [REDACTED]

The number of hours of stimulation delivered (Group #1 only) as measured by the stimulator will be recorded throughout the study. [REDACTED]

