Exclusion Criteria	
 • Body Mass Index (BMI) > 40 kg/m² • Conditions that place the subject at increased risk of infection in the opinion of the investigator, [REDACTED] • History of valvular heart disease • Implanted cardiac pacemaker/defibrillator or Deep Brain Stimulator • Bleeding disorder OR INR ≥ 1.5 for those on warfarin (Group #1, only) • Confounding conditions [REDACTED] [REDACTED] or central nervous system disorders • History of nerve damage [REDACTED] • Allergy to skin surface electrodes and/or medical-grade adhesive tapes • Contraindications to the proposed anesthetic protocol during lead placement [REDACTED] • Any other medical condition that may interfere with ability to participate in a clinical trial as determined by the Investigator • Prisoners, minors or individuals that report to investigators (e.g., students, employees) • Pregnant (Group #1, only) • History of substance abuse within 6 months • Potential secondary gain issues (e.g., pending claims or receiving disability)
Primary Safety Endpoint	Occurrence of device-related adverse events.
Primary Clinical Endpoint	
The primary clinical endpoint is average daily pain while walking. Subjects will record [REDACTED] pain while walking [REDACTED] in a daily diary [REDACTED]
 
[REDACTED] The difference in the [REDACTED] pain scores between the two groups (Treatment vs. Control) will be calculated to determine if PNS Therapy provides a [REDACTED] reduction in [REDACTED] daily pain while walking.

Secondary Endpoints	Pain-related outcomes

	
 • Pain intensity over the last 24 hours as recorded as Average pain [REDACTED] • Pain intensity [REDACTED] • Pain right now [REDACTED] • Cumulative analgesic usage [REDACTED] • Opioid-related side effects [REDACTED] 
Functional outcomes
 
 • Timed Up and Go [REDACTED] • 6 minute walk test [REDACTED] • Change in pain, physical function, and stiffness [REDACTED] • Patient Global Impression of Change (PGIC) [REDACTED] • Pain Catastrophizing Scale (PCS) [REDACTED] • Time to meet recovery milestones [REDACTED] • [REDACTED] 
Subject Satisfaction Survey
 
 • Inpatient Pain Management Experience Survey [REDACTED] • Compliance [REDACTED] • [REDACTED] 
Physical Therapy Sessions

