5.3 Secondary Outcomes

Secondary outcome measures will provide additional information on pain and function.

The [REDACTED] is a widely used assessment designed to measure pain intensity and the interference of pain on daily activities and moods [REDACTED]

Cumulative Analgesic usage

The amount and type of analgesic used by the subject will be recorded daily in a diary before TKA surgery, from the subject's records during their hospital stay, in daily diaries after discharge from the hospital, and at each visit following End of Treatment.

Opioid-related Side Effects

Opioid pain medications are associated with a wide variety of side effects. Common side effects include nausea and vomiting, constipation, urinary retention, pruritus, drowsiness, and respiratory depression.

Timed Up and Go [REDACTED]

The [REDACTED] is an objective measure of mobility. [REDACTED]

Six minute walk test [REDACTED]

The [REDACTED] records the total distance the subject can walk in 6 minutes. [REDACTED]

The [REDACTED] is a widely-used validated questionnaire to evaluate patients with osteoarthritis of the knee and consists of 24 items evaluating pain (5 items), stiffness (2 items), and physical functional disability (17 items) [REDACTED]

Patient Global Impression of Change (PGIC)

Participant ratings of global improvement are one of the core outcome domains in chronic pain studies (Dworkin *et al.* 2005). [REDACTED]

Pain Catastrophizing Scale (PCS)

The PCS is a widely-used, validated and reliable 13-question instrument to assess rumination (4 questions), magnification (3 questions), and helplessness (6 questions) (Sullivan, 2009.; Osman *et al.* 1997). [REDACTED]

Time to Meet Recovery Milestones

The time until the subject meets criteria related to hospital discharge will be measured. [REDACTED]

Subject Satisfaction Survey

A survey will be administered to assess subject satisfaction with the study and postsurgical pain therapies.

Inpatient Pain Management Experience Survey

This survey is comprised of a subset of questions from the Hospital Consumer Assessment of Healthcare Providers and Systems. This survey will be administered to assess subject satisfaction with pain management during their time in the hospital for TKA surgery.

Compliance

SPRINT Beta stimulator [REDACTED]

[REDACTED] subject compliance [REDACTED]

Physical Therapy Sessions

[REDACTED] physical therapy sessions

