10.4 Per Protocol and Intent to Treat Analyses

Analyses of the primary and secondary effectiveness endpoints will be conducted on the intent-to-treat (ITT) population and the per-protocol (PP) population at each specified study interval defined as follows:

PP Population: [REDACTED]

ITT Population: [REDACTED]

[REDACTED]

[REDACTED]

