12.0 Adverse Events and Unanticipated Adverse Device Effects

Adverse events (AEs) that occur during the study will be captured on CRFs. Specific details regarding any observed AE will be collected on a separate Adverse Event Form. The severity of each Adverse Event will be collected as well as its relationship to the System. AEs will be classified as mild (event that causes mild discomfort or inconvenience and resolves without treatment), moderate (event that requires medical intervention or medication to treat), or severe (event that requires intervention to prevent permanent impairment or damage, an event that requires or prolongs hospitalization, or an event that is disabling, causing permanent damage, life threatening, or causing death). Adverse events will also be classified as serious or non-serious. Any necessary treatment or intervention required and the resolution status of the adverse event will also be documented. Adverse Events will be followed to resolution. Side effects from narcotic therapy will be collected but not reported as adverse events. Common symptoms after TKA surgery related to the normal healing process (i.e., swelling, bruising, stiffness, incision tenderness, drainage, etc.) will also not be reported as adverse events unless they meet the definition and criteria for AE reporting

An Adverse Device Effect (ADE) is a device-related Adverse Event. All ADE's are further categorized as anticipated or unanticipated. Any ADE's specified in the Risk Analysis of this Investigational Plan will be considered "anticipated". All other ADE's are considered "unanticipated". Anticipated events that occur with a greater frequency than expected are also considered unanticipated.

An Unanticipated Adverse Device Effect (UADE) is defined as any serious adverse effect on health or safety or any life threatening problem or death caused by, or associated with, a device, if that effect, problem or death was not previously identified in nature, severity or degree of incidence in this Investigational Plan or application or any other unanticipated serious problem associated with a device that relates to the rights, safety or welfare of subjects.

Table 2 Unanticipated Adverse Device Event Sponsor Contact Information

UNANTICIPATED ADVERSE DEVICE EVENT SPONSOR CONTACT INFORMATION			
Name/Title	Email address	Telephone Number	Fax Number
[REDACTED]	[REDACTED]	[REDACTED]	[REDACTED]
[REDACTED]	[REDACTED]	[REDACTED]	[REDACTED]

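### Opioid side effects are queried in subjects taking opioids and then compared between groups; with the denominator not visible, either way of counting subjects off opioids can distort the comparison

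*Combined protocol and SAP*

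**What the plan says.** The Synopsis (Section 2.0) lists "Opioid-related side effects [REDACTED]" among the pain-related secondary endpoints; its definition is blacked out. Section 5.3 describes the kind of event meant: "Common side effects include nausea and vomiting, constipation, urinary retention, pruritus, drowsiness, and respiratory depression".

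On collection, Section 10.1 states that "subjects taking opioids [REDACTED] will be queried for side effects associated with opioids". There are redactions immediately before, inside and immediately after that sentence. On analysis, the same paragraph ends: "These pain treatment and analgesic-related outcomes will be compared between the Groups".

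Three other places bear on the point:

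- Section 10.4 sets the analysis populations: "Analyses of the primary and secondary effectiveness endpoints will be conducted on the intent-to-treat (ITT) population and the per-protocol (PP) population". Both definitions are redacted.
- Analgesic use is a secondary outcome in its own right. Section 5.3 says "The amount and type of analgesic used by the subject will be recorded daily in a diary before TKA surgery", with recording continued in hospital, after discharge and at later visits. Section 10.1 adds: "Changes in opioid usage may be calculated using morphine equivalent dosing (MED)".
- Section 12.0 says: "Side effects from narcotic therapy will be collected but not reported as adverse events".

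**The concern.** Randomisation takes place at Visit 1 (Section 8.5.1), and Group #1 receives stimulation both before and after surgery. Opioid use from lead placement onward is therefore a post-randomisation state. The background section presents the therapy as a non-narcotic way of reducing pain, and analgesic use is a separate endpoint, so the plan itself treats opioid use as something the therapy may change.

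The visible rule makes the side-effect question depend on that state. A subject who has stopped opioids, or never needed them, may have no side-effect record at all. Such subjects must then be either left out of the comparison or scored without having been asked. Leaving them out gives a comparison of non-randomised subsets, which may shrink at different rates in the two groups during recovery. Scoring them unasked means that nausea, constipation or drowsiness, none of which is specific to opioids, is looked for in users and assumed absent in non-users.

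The adverse-event pages are no visible substitute, because narcotic side effects are kept out of adverse-event reporting. A symptom that was never asked about cannot be recovered at analysis.

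**Working it through.** The documents give no opioid-use rate, side-effect rate, effect size or power for this endpoint, so there is no planned figure to reproduce. All rates below are assumptions, chosen to show direction and range.

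**Step 1. Users-only against all randomised.** Let *u* be the proportion taking opioids at a contact and *s* the proportion of users with a side effect. If subjects off opioids truly have none, the rate over all randomised subjects is *u* × *s*; the users-only rate is *s*.

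| Assumption | Control | Group #1 | All randomised | Users only |
|---|---|---|---|---|
| Same *s* in both groups | *u* = 0.80, *s* = 0.50 | *u* = 0.50, *s* = 0.50 | 0.40 vs 0.25 | 0.50 vs 0.50 |
| Remaining Group #1 users are worse off | *u* = 0.80, *s* = 0.50 | *u* = 0.50, *s* = 0.60 | 0.40 vs 0.30 | 0.50 vs 0.60 |

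In the first row a 15-point difference becomes zero. In the second, a 10-point advantage for Group #1 becomes a 10-point disadvantage.

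**Step 2. How a reversal can arise without harm.** Suppose side effects occur in 40% of light users and 80% of heavy users in both groups. Control has 40% light and 40% heavy users; Group #1 has 10% light and 30% heavy.

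- All randomised: control 0.40 × 0.40 + 0.40 × 0.80 = 0.48; Group #1 0.10 × 0.40 + 0.30 × 0.80 = 0.28.
- Users only: 0.48 / 0.80 = 0.60 against 0.28 / 0.40 = 0.70.

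Group #1 has fewer users of both kinds, yet looks worse among users.

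**Step 3. Range.** With equal *s* in the two groups, the users-only difference is always zero. The all-randomised difference is (*u* control − *u* Group #1) × *s*. For *s* from 0.40 to 0.80:

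- use of 90% vs 70%: 0.20 × 0.40 = 8 points to 0.20 × 0.80 = 16 points;
- use of 80% vs 40%: 0.40 × 0.40 = 16 points to 0.40 × 0.80 = 32 points.

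With 25 per group (50 subjects, 1:1 assumed because the ratio is not visible) and two-sided 5% tests, power over these cases runs from about 9% to about 63%. Even the all-randomised comparison would be imprecise.

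**Step 4. Scoring non-users as none without asking.** Suppose 30% of all subjects have a symptom on the list, unrelated to opioids, and use is 80% vs 50%. Asking users and entering zero for the rest gives 0.80 × 0.30 = 24% against 0.50 × 0.30 = 15%. This is a 9-point advantage for Group #1 where none exists.

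**Step 5. Asking everyone.** Under Step 4 the result is 30% vs 30%, which is correct. Now combine the two assumptions: 50% of users and 30% of non-users report a symptom, in both groups.

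- Control: 0.80 × 0.50 + 0.20 × 0.30 = 0.46.
- Group #1: 0.50 × 0.50 + 0.50 × 0.30 = 0.40.

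The difference in symptom burden is 6 points. Users-only shows 0. Unasked zeros show 40% vs 25%, or 15 points; the excess of 9 points is the difference in use times the background rate, 0.30 × 0.30.

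**The case against.** The strongest reply is that Section 10.1 says who is asked, not who is analysed. Section 10.4 puts secondary effectiveness endpoints on ITT and PP populations, and no visible text provides for a users-only analysis. A subject taking no opioid cannot have a current opioid side effect, and opioid use is recorded for everyone, so non-users can be entered as none from data already held. The redactions sit exactly where such a rule would be written.

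Much of this stands. A reader might infer that side effects are asked of users and nobody else, or that the comparison is confined to users. Neither is stated; both are inferences across blacked-out text. A reader might also infer that any benefit from getting subjects off opioids is lost. The documents do not support that: lower opioid use is compared as its own secondary outcome, and lower doses among continuing users could still show as fewer side effects.

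What does not stand is that counting non-users as none settles the matter. It is logical for a side effect known to be caused by an opioid. The listed symptoms, however, also occur for other reasons after surgery, and asking users alone cannot separate the causes (Step 4). An ITT definition would fix which subjects belong to the population, but need not say how an unasked subject is scored.

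A further fair point is that asking everyone brings background postoperative symptoms into the measure. In Step 5 the visible difference falls from 15 to 6 points. Under those assumptions 6 points is the actual difference in symptoms, but background symptoms do make it harder to detect in about 50 subjects.

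**Conclusion.** The concern holds as a weakness in the visible collection rule, not as a demonstrated error in the analysis. Collection is tied to a post-randomisation state and the result is compared between groups. The denominator is not known, but both plausible choices can mislead, in different ways: a users-only comparison can hide or reverse a reduction in side effects that comes from stopping opioids, and unasked zeros can favour the group using fewer opioids.

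Under the assumed figures, the first turns 40% vs 25% into 50% vs 50%, and the second turns no difference into 24% vs 15%. The sizes rest wholly on assumed rates of opioid use and symptoms, and on use differing between groups. If use is the same in both groups and the users are alike, neither distortion arises. The point concerns one secondary endpoint and does not touch the primary outcome or the analgesic-usage comparison. It is a cheap improvement, worth making because the missing answers cannot be collected afterwards.

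**What to change.** In Section 10.1 and on the CRF:

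1. Ask every subject in both groups the same symptom questions at each scheduled contact where side effects are assessed, whether or not opioids are being taken.
2. Record current opioid use alongside the answers.
3. Make the between-group comparison over all randomised subjects with data at that contact.
4. As a supportive analysis, count subjects not taking opioids as having no opioid-related side effect.
5. Report users-only figures as descriptive, with the number of users in each group.

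If the redacted text already contains these rules, it is enough to confirm that.

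The cost is a CRF wording change, a short addition to Section 10.1, and a few more questions for subjects off opioids at contacts already in Table 1 of Section 8.6. No visit is added. The drawback is that some background postoperative symptoms enter the measure; the supportive analysis and the recorded opioid use help the reader judge how much.

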10.2 Plan to maximize subject retention and minimize loss of data

Significant efforts will be made to maintain maximum subject retention and follow up data and minimize the percentage of missing data.

10.3 Safety Endpoint Analysis

Adverse events will be documented (as defined in Section 12.0), reported, and categorized so that the safety profile of this approach may be further understood. Knowledge gained from this study will further refine consent forms and the risk benefit profile for future studies.

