3.4 Study Objective

To compare the effectiveness and safety of PNS therapy in conjunction with the SOC to SOC alone for the treatment of knee pain following TKA.

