4.0 Introduction and background

4.1 Introduction

The goal of this research is to gather data regarding the safety and effectiveness of PNS therapy for the treatment of pain following total knee arthroplasty (TKA; a.k.a. total knee replacement).

stimulation will [REDACTED] produce greater pain relief than with standard of care alone.

4.2 *Background*

Postoperative pain following total knee arthroplasty is a substantial medical problem

Present treatments for postoperative TKA pain are ineffective, carry risks of side effects/complications, and/or are not indicated for extended use.

[figure not shown]
The proposed non-narcotic therapy may reduce postoperative pain with minimal risk of infection and falls

The proposed method aims to relieve postoperative pain following TKA by delivering electrical stimulation through percutaneous [REDACTED] SPRINT MicroLeads

The proposed therapy may provide immediate pain relief following TKA that can be delivered for several weeks as patients continue their postsurgical recovery

The proposed method may provide immediate pain relief [REDACTED]

The proposed method has been [REDACTED] used to [REDACTED]
[REDACTED] reduce chronic pain in patients with lower limb amputations

The proposed method to treat postoperative pain following TKA has been tested as a treatment for chronic pain in individuals with lower limb amputations [REDACTED]

Electrical stimulation was delivered through [REDACTED] leads [REDACTED]

The proposed method has been tested to treat pain in patients following TKA in separate preliminary studies.

[REDACTED]

Summary

[REDACTED]

The proposed study will determine if this therapy in combination with the site's respective SOC can produce significant reductions in postoperative pain following TKA as compared to the site's SOC alone.

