5.5 Safety Endpoint

The primary safety endpoint is the occurrence of protocol-related adverse events.

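### Section 3.4 sets a comparative safety objective, but the primary safety endpoint rests on attribution and Section 10.3 prespecifies no comparison of adverse events between the groups

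*Combined protocol and SAP*

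**What the plan says.** - **Objective.** Section 3.4 is comparative for safety as well as effectiveness: "To compare the effectiveness and safety of PNS therapy in conjunction with the SOC to SOC alone".
- **Primary safety endpoint.** The synopsis gives "Occurrence of device-related adverse events". Section 5.5 gives a different set: "The primary safety endpoint is the occurrence of protocol-related adverse events".
- **Safety analysis.** Section 10.3 states "Adverse events will be documented (as defined in Section 12.0), reported, and categorized" and adds that this will help describe the safety profile and inform later consent forms. It reads as a complete paragraph and carries no redaction mark.
- **Capture.** Section 12.0 puts adverse events occurring in the study on the CRF, without limiting them to Group #1 or to attributed events. On causality it says "The severity of each Adverse Event will be collected as well as its relationship to the System". Opioid side effects are recorded separately. Normal-healing symptoms are left out unless they meet the adverse event criteria.
- **Comparisons written elsewhere.** For analgesic outcomes, Section 10.1 says "These pain treatment and analgesic-related outcomes will be compared between the Groups". Section 10.4 says "Analyses of the primary and secondary effectiveness endpoints will be conducted on the intent-to-treat (ITT) population", and names the per-protocol population as well. No safety population is visible, but part of that section is redacted.

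**The concern.** A comparative objective needs an analysis that uses the control group. A device-related count cannot do that, because Group #2 has no device. Whether an event in Group #1 enters the endpoint depends on a case-by-case judgement. Only Group #1 has leads placed and no sham or blinding is visible, so that judgement would presumably be made knowing who has them.

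This matters most for harms that can follow knee replacement with or without leads, such as infection and falls. For a single case, surgery and device can both be plausible causes. Comparing how often such events occur in each randomised group avoids having to decide. Without that comparison, a low attributed count could be read as safety relative to SOC although the control rate was never used.

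**Working it through.** The plan gives no safety rate, margin or power, so there is no stated figure to reproduce. The first check is of the text.

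1. *Question asked* (Section 3.4): is PNS plus SOC as safe as SOC alone? This needs event frequencies in both groups.
2. *Endpoint, synopsis wording*: device-related events. The Group #2 count is zero by definition, so this wording carries no comparison.
3. *Endpoint, Section 5.5 wording*: protocol-related events. These could arise in Group #2, for example a fall during a study walking test. The count still depends on attribution, and the visible text does not define the term.
4. *Analysis* (Section 10.3): it covers adverse events as Section 12.0 defines them, so it is wider than the endpoint. It states no comparison by group.
5. *Result*: an infection or fall put down to surgery is recorded and reported, is not counted as device-related, and enters no prespecified contrast.

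The second check is what a comparison could deliver. Inputs: about 50 subjects (synopsis; Section 7.2 says up to 50). The allocation ratio is not visible, so 25:25 and 33:17 are assumed as a range. All event rates and counts below are assumptions for illustration.

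*Upper bound when no events are seen*, n treated:
- Two-sided 95%, n = 25: 1 − 0.025^(1/25) = 0.137, or 13.7%.
- One-sided 95%, n = 25: 1 − 0.05^(1/25) = 0.113, or 11.3%.
- One-sided 95%, n = 33: 1 − 0.05^(1/33) = 0.087, or 8.7%.

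*Exact power of Fisher's test*, two-sided alpha 0.05, summing the probabilities of all outcomes with p ≤ 0.05:

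| Control vs treatment rate | 25:25 | 33:17 (treatment:control) |
|---|---|---|
| 2% vs 10% | 2% | 1% |
| 5% vs 15% | 7% | 5% |
| 5% vs 20% | 20% | 16% |
| 5% vs 40% | 82% | 78% |

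By the normal approximation with pooled variance, 80% power for 5% versus 20% needs 76 per group.

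*Example interval*, 5/25 versus 1/25, Newcombe. The Wilson limits are 0.089 to 0.391 and 0.007 to 0.195, and the difference is 0.20 − 0.04 = 0.16.
- Lower: 0.16 − √[(0.20 − 0.089)² + (0.195 − 0.04)²] = −0.03.
- Upper: 0.16 + √[(0.391 − 0.20)² + (0.04 − 0.007)²] = 0.35.

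So even five events against one leaves an interval of −3 to +35 percentage points. For 5/25 versus 0/25, Fisher's two-sided p is 2 × C(25,5)/C(50,5) = 2 × 53,130/2,118,760 = 0.0502. A test would add little; the table and interval are the useful output.

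**The case against.** **Data capture.** A reader might infer that an excess of infections or falls put down to surgery would go unseen. The documents do not support that. Section 12.0 captures such events with severity, seriousness and outcome, neither infection nor falls is among the excluded healing symptoms, and Section 10.3 reports them. The data would exist by group, and nothing forbids comparing them. What is missing is the commitment to do so.

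**Endpoint.** A reader might also infer that the endpoint is zero in Group #2 under any reading. That is true only of the device-related wording.

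**Bias.** An all-cause comparison is not free of bias in this design. The bleeding/INR and pregnancy exclusions apply to Group #1 only (Section 8.3.2). Group #1 subjects whose lead placement fails may leave the study (Section 8.5.2). Lead placement and device-related unscheduled visits give Group #1 more occasions on which events can be noticed. It would be wrong to call the comparison the only unbiased answer, but these limits can be stated and partly handled.

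**Size.** The zero-event bound comes from the sample size, not from attribution; an all-cause endpoint with 0/25 would have the same bound. This stands, and it is why the remedy is descriptive.

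**Status of the objective.** Only Section 3.4 words safety as a comparison. The synopsis objective and Section 8.1 do not mention safety, and Section 4.1 speaks of gathering data. Section 3.4 is nevertheless the stated study objective. The background line that the therapy "may reduce postoperative pain with minimal risk of infection and falls" is rationale; no text plans to conclude it from a low attributed count.

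**Redaction.** Parts of Sections 10.4 and 13.2 are redacted and Appendix A is not shown. A safety population may be defined there, but a population alone would not supply the comparison absent from Section 10.3.

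**Conclusion.** The point holds in this form: the plan sets a comparative safety objective, defines its primary safety endpoint by attribution in two inconsistent ways, and prespecifies no between-group analysis of adverse events. The consequence is a safety question without a planned answer; it is not a loss of data. A reader should not go further and conclude that surgical-type events would be hidden, or that a comparison would settle the matter.

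With about 50 subjects, only a very large excess could be detected reliably (roughly 5% versus 40% at 25:25). With 25 treated and no events, rates up to 13.7% remain compatible with the data. These sizes rest on the assumed allocation and event rates. The textual finding rests on the visible text and on Section 10.3 being complete as it reads.

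**What to change.** Rewrite Section 10.3 as follows.

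- Report the number of subjects with at least one adverse event, and with at least one serious adverse event, regardless of attribution, by randomised group. Use the same windows in both groups (for example surgery to 4 weeks, and Visit 1 to 12 months). Give the risk difference with a 95% CI, and do not rely on a significance test.
- Show infection and falls as all-cause categories in the same table.
- Keep all randomised subjects in the denominators, and state how Group #1 subjects terminated after failed lead placement are counted in each window.
- Name the Group #1-only exclusions and extra contacts as limits on the comparison.
- Reconcile the synopsis and Section 5.5 wordings of the endpoint, then report the attributed events as a Group #1 rate with an exact 95% CI.
- Limit the safety conclusion to what the intervals support.

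The cost is a change of wording and one or two tables built from data already planned for the CRF. The intervals will be wide, so the safety statement will be less favourable than an attributed count alone would suggest.
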